4.1.1 Inclusion Criteria

Patients must meet the following criteria for study entry:

- Willingness and ability to provide signed informed consent
 - Additionally, at U.S. sites, patients must provide Health Insurance Portability and Accountability Act (HIPAA) authorization, and in other countries, as applicable according to national laws.
- Willingness and ability to undertake all scheduled visits and assessments
- Previous enrollment in and completion of study treatment and the Week 96 visit of either Study GX29185 or Study GX29176, without early treatment discontinuation (lampalizumab or sham)
- For women of childbearing potential: agreement to remain abstinent (refrain from heterosexual intercourse) or use contraceptive methods *with* a failure rate of < 1% per year during the treatment period and for at least 30 days after the last dose of lampalizumab.

A woman is considered to be of childbearing potential if she is postmenarcheal, has not reached a postmenopausal state (≥ 12 continuous months of amenorrhea with no identified cause other than menopause), and has not undergone surgical sterilization (removal of ovaries and/or uterus).

Examples of contraceptive methods with a failure rate of < 1% per year include bilateral tubal ligation, male sterilization, established proper use of hormonal contraceptives that inhibit ovulation, hormone-releasing intrauterine devices, and copper intrauterine devices.

The reliability of sexual abstinence should be evaluated in relation to the duration of the clinical trial and the preferred and usual lifestyle of the patient. Periodic abstinence (e.g., calendar, ovulation, symptothermal, or postovulation methods) and withdrawal are not acceptable methods of contraception.

- For men: agreement to remain abstinent (refrain from heterosexual intercourse) or use contraceptive measures and agreement to refrain from donating sperm, as defined below:

With female partners of childbearing potential, men must remain abstinent or use a condom plus an additional contraceptive method that together result in a failure rate of < 1% per year during the treatment period and for at least 120 days after the last dose of study drug. Men must refrain from donating sperm during this same time period.

With pregnant female partners, men must remain abstinent or use a condom during the treatment period and for at least 120 days after the last dose of study drug to avoid exposing the embryo.

The reliability of sexual abstinence should be evaluated in relation to the duration of the clinical trial and the preferred and usual lifestyle of the patient. Periodic abstinence (e.g., calendar, ovulation, symptothermal, or postovulation methods) and withdrawal are not acceptable methods of contraception.

- For patients participating in microperimetry (at selected sites only): must have participated in the microperimetry testing during the parent study

4.1.2 Exclusion Criteria

Patients who meet any of the following criteria will be excluded from study entry:

- Concurrent ocular conditions exclusion criterion
History of other ocular diseases that give reasonable suspicion of a disease or condition that contraindicates the use of lampalizumab or that might affect interpretation of the results of the study or that renders the patient at high risk of treatment complications
- Concurrent systemic conditions exclusion criteria
History of other diseases, metabolic dysfunction, physical examination finding, or clinical laboratory finding that gives reasonable suspicion of a disease or condition that contraindicates the use of lampalizumab or that might affect interpretation of the results of the study or that renders the patient at high risk of treatment complications
Predisposition to or history of increased risk of infection (e.g., history of splenectomy or chronic immunosuppression)
Requirement for continuous use of any medications or treatments indicated in the “Excluded Therapy” section of the protocol (see Section 4.4.2)
Pregnancy or lactation, or intention to become pregnant during the study
Women of childbearing potential must have a negative urine pregnancy test result at the Day 1 visit prior to initiation of study drug.

4.2 METHOD OF TREATMENT ASSIGNMENT

This is an open-label study. All patients enrolled in the extension study will receive 10 mg *intravitreal* injections of lampalizumab Q4W or Q6W.

A patient must satisfy all eligibility criteria (see Sections 4.1.1 and 4.1.2) at the Day 1 visit (first study treatment) and sign informed consent for enrollment. All patients enrolled will receive lampalizumab treatment at the same dosing frequency as their originally assigned dosing frequency in the parent study.

4.3 STUDY TREATMENT

The investigational medicinal product (IMP) for this study is lampalizumab.

4.3.1 Lampalizumab Formulation, Packaging, Storage, and Handling

Please see the Lampalizumab Investigator's Brochure for the lampalizumab clinical formulation. See the Pharmacy Manual for additional specifics regarding the lampalizumab formulation, product packaging, storage, and handling.

4.3.2 Lampalizumab Dosage, Administration, and Compliance

4.3.2.1 Dosage

A 10-mg dose of lampalizumab will be used in the extension study and will be administered by *intravitreal* injection to all enrolled patients either Q4W or Q6W during the treatment period (see [Appendix 1](#) for the study flowchart).

The lampalizumab injections should not be repeated earlier than 22 days from previous dosing. Missed doses of study drug will not be made up *unless the missed dose is due to an unexpected issue, such as those listed in Section 3.1.1*.

4.3.2.2 Administration

The detailed instructions for lampalizumab reconstitution for the pre-injection procedure, *intravitreal* administration, and post-injection procedure for the study eye are provided in the Pharmacy Manual.

Guidelines for treatment interruption or discontinuation are provided in Section [5.1](#) and [Table 1](#).

Any overdose or incorrect administration of study drug should be noted on the Study Drug Administration eCRF. Adverse events associated with an overdose or incorrect administration of study drug should be recorded on the Adverse Event eCRF.

4.3.2.3 Compliance

This study will be conducted in accordance with the U.S. Food and Drug Administration (FDA) regulations; the International Conference on Harmonisation (ICH) E6 Guideline for Good Clinical Practice (GCP); and applicable local, state, and federal laws, as well as other applicable country laws.

4.3.3 Investigational Medicinal Product Accountability

All IMPs required for completion of this study (lampalizumab) will be provided by the Sponsor. The study site will acknowledge receipt of IMPs, using the IxRS to confirm the shipment condition and content. Any damaged shipments will be replaced.

IMPs will either be disposed of at the study site according to the study site's institutional standard operating procedure or will be returned to the Sponsor with the appropriate documentation. The site's method of IMP destruction must be agreed to by the Sponsor. The site must obtain written authorization from the Sponsor before any IMP is destroyed, and IMP destruction must be documented on the appropriate form.

Accurate records of all IMPs received at, dispensed from, returned to, and disposed of by the study site should be recorded on the Drug Inventory Log.

4.3.4 Post-Trial Access to Lampalizumab

The Sponsor will offer post-trial access to the study drug (lampalizumab) free of charge to eligible patients in accordance with the Roche Global Policy on Continued Access to Investigational Medicinal Product, as outlined below.

A patient will be eligible to receive study drug after completing the study if all of the following conditions are met:

- The patient has a sight-threatening or severe medical condition and requires continued study drug treatment for his or her well-being.
- There are no appropriate alternative treatments available to the patient.
- The patient and his or her doctor comply with and satisfy any legal or regulatory requirements that apply to them.

A patient will not be eligible to receive study drug after completing the study if any of the following conditions are met:

- The study drug is commercially marketed in the patient's country and is reasonably accessible to the patient (e.g., is covered by the patient's insurance or would not otherwise create a financial hardship for the patient).
- The Sponsor has discontinued development of the study drug or data suggest that the study drug is not effective for GA.
- The Sponsor has reasonable safety concerns regarding the study drug as treatment for GA.
- Provision of study drug is not permitted under the laws and regulations of the patient's country.

The Roche Global Policy on Continued Access to Investigational Medicinal Product is available at the following Web site:

http://www.roche.com/policy_continued_access_to_investigational_medicines.pdf

4.4 CONCOMITANT THERAPY

Patients who use other maintenance therapies should continue their use. Patients required to use medications that are prohibited will not be eligible for enrollment or continuation in the study (see Section 4.4.2).

Concomitant therapy includes any prescription drugs or over-the-counter preparations other than protocol-specified procedural medications (e.g., dilating drops) and pre- and post-study treatment medications (e.g., proparacaine or anti-microbials [if applicable]) used by a patient from the time of study enrollment at the Day 1 visit through the conclusion of the patient's study participation or early termination visit. All concomitant

medications should be reported to the investigator and recorded on the Concomitant Medications eCRF log except for Lucentis® for treatment of either eye (if applicable), which will have a separate eCRF log.

4.4.1 Permitted Therapy

Patients required to use medications that are prohibited (see Section 4.4.2) will not be eligible for the study or continuation of the study. Of note, the following are examples of some common therapies that are permitted:

- Onset of ocular hypertension or glaucoma in either eye during a patient's study participation should be treated as clinically indicated.
- Onset of cataract or posterior capsular opacification in either eye during the patient's study participation may be treated as clinically indicated. Dose interruption criteria (see Section 5.1.2 and Table 1) may apply with cataract surgery.
- Short-term use of topical corticosteroids may be administered (e.g., after cataract surgery, yttrium aluminum garnet capsulotomy, or peripheral iridotomy).
- At the discretion of the investigator, patients may be treated with Lucentis if they are diagnosed with an ocular condition in either eye for which Lucentis is approved in the patient's country. Consult the region-specific Lucentis prescribing information for dosing, frequency, and administration guidance.

Note: If, in the opinion of the investigator, treatment with Lucentis should be given (in either eye) at the same visit during which study treatment will be administered, treatment with Lucentis must be administered first. Following this, the safety assessments (including IOP check) must be performed prior to calling IxRS for the study treatment kit assignment and prior to lampalizumab injections. Individual trays and separate sterile preparation must be prepared and separately performed for each treatment.

- Oral corticosteroids at doses ≤ 10 mg/day of prednisone or equivalent may be administered. The dose-holding criteria apply to doses > 10 mg/day (see Section 5.1.2 and Table 1).
- *Prophylactic use of systemic antibiotics (e.g., for prevention of urinary tract infection [UTI]) should be discussed with Medical Monitor.*

4.4.2 Excluded Therapy

At the discretion of the investigator, patients may continue to receive medications and standard treatments administered for other conditions. However, the following medications and treatments are prohibited from use during a patient's study treatment, and patients discontinue the study drug and the study to receive these therapies:

- Investigational therapy other than study drug
- Systemic anti-vascular endothelial growth factor (anti-VEGF) agents
- *Intravitreal* anti-VEGF agents (other than Lucentis) in either eye
- *Intravitreal*, subtenon, or chronic topical (ocular) corticosteroids in study eye

- Systemic or intravenous immunomodulatory therapy (e.g., azathioprine, methotrexate, mycophenolate mofetil, cyclosporine, cyclophosphamide, antitumor necrosis factors, eculizumab)
- Treatment with Visudyne® in study eye
- Other experimental therapies (except those with vitamins and minerals)

4.5 STUDY ASSESSMENTS

Please see [Appendix 1](#) for the schedule of assessments performed during the study.

4.5.1 Informed Consent Forms

Written informed consent for participation in the study must be obtained before performing any study-related procedures. Informed Consent Forms (ICFs) for enrolled patients will be maintained at the study site.

At the sites where investigator intends to ask his/*her* patients to self-administer antimicrobials pre- and post-injection, the ICF needs to be signed at an earlier date (e.g., Week 90 or 92 visit in parent study) in order to allow the ICF to be in place prior to the patient receiving pre-injection antimicrobials. In addition, during the Week 96 visit, if the ICF is signed prior to completion of the Week 96 assessments of the parent study, then the Week 96 parent study blood draws and the Day 1 OLE blood draw can be performed at the same time.

All parent-study Week 96 evaluations must be completed and reviewed to confirm that patients meet all eligibility criteria prior to enrollment at the Day 1 visit in this extension study. The investigator will maintain a log to record details of all patients who sign the ICF to confirm patient's eligibility or ineligibility to be enrolled in the study as applicable.

4.5.2 Medical History and Demographic Data

Medical history and demographic data were collected during the parent studies and will not need to be *obtained again* during the OLE *study*.

4.5.3 Vital Signs

Vital signs will be collected at the early termination visits and will include measurements of temperature, respiratory rate, pulse rate, and systolic and diastolic blood pressure while the patient is in a seated position after resting for 5 minutes.

4.5.4 Other Disease-Specific Assessments

4.5.4.1 Ocular Assessments

Ocular assessments include the following:

- BCVA on ETDRS chart at a starting distance of 4 m (perform prior to dilating eyes; see [Appendix 4](#))
- BCVA assessed by ETDRS chart at a starting distance of 4 m (perform prior to dilating eyes; see [Appendix 5](#)) under low luminance conditions

- MNRead charts (see [Appendix 14](#) for details on specific countries where test will be administered) or Radner Reading Charts (see [Appendix 15](#) for details on specific countries where test will be administered; perform prior to dilating eyes). The test will be administered first monocularly (right/left eye) and then binocularly (both eyes).
- Pre-injection IOP measurement for both eyes (perform prior to dilating eyes; the method used for this assessment must remain consistent throughout the study)
- Slit-lamp examination (for the definition of ocular inflammation, see Section [5.3.5](#); for inflammation grading scales, see [Appendix 3](#))
- Dilated binocular indirect ophthalmoscopy
- Finger-counting, hand-motion, or light-perception tests performed by the investigator within 15 minutes post-injection for the study eye only. A finger-counting test will be conducted for each patient by the physician within 15 minutes following study treatment; hand-motion and light-perception tests will be performed when necessary.
- Following the study treatment, IOP will be measured between 30 and 50 minutes after study treatment by qualified site staff (except for the VA examiner) for the study eye only; if the IOP is increased by ≥ 10 mmHg from the pre-injection IOP value, IOP will be measured again at 60–80 minutes post-injection. If there are no safety concerns, the patient will be permitted to leave the clinic. If the IOP value is of concern to the investigator, the patient will remain in the clinic and will be managed in accordance with the investigator’s clinical judgment. Both the last post-injection IOP measured prior to any intervention for increased IOP (if applicable) and the last post-intervention IOP value (if applicable) will be recorded on the appropriate eCRF. If applicable, an Adverse Event eCRF should also be completed (see Section [5.2.1](#)).

Note: If the study eye is treated with a Lucentis injection during the same visit that study treatment is administered, the treatment with Lucentis must be performed first. The post-Lucentis treatment IOP is to be measured and recorded on the eCRF, irrespective of the subsequent study treatment administration.

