5. ASSESSMENT OF SAFETY

5.1 SAFETY PLAN

Lampalizumab is not an approved drug and is currently in clinical development. Thus, the full safety profile is not completely known at this time. The safety plan for patients in this study is based on clinical experience with lampalizumab in completed and ongoing studies. The safety plan for this study is designed to help minimize patient risk and will include specific monitoring assessments as detailed below. The incidence and characteristics of adverse events and serious adverse events will be assessed as described in this protocol. Detailed ocular examinations, including indirect ophthalmoscopy and slit-lamp examination, will be performed throughout the study.

Potential ocular safety issues currently thought to be associated with the route of administration or pharmacology of lampalizumab include decreased BCVA, conjunctival hemorrhage, ocular inflammation (see Section 5.3.5 and Appendix 3 for anterior chamber and vitreous inflammation grading scales), intraocular infection (endophthalmitis), transient and/or sustained elevation of IOP, transient vision loss, cataract development or progression, retinal or vitreous hemorrhage, and retinal break or detachment. The occurrence of all adverse events (serious and non-serious) and pregnancies will be recorded for the duration of this study.

Systemic levels of lampalizumab following multiple *intravitreal* administrations are anticipated to be low. Systemic side effects of lampalizumab are not anticipated based on nonclinical data and clinical studies conducted to date, but are possible. As part of the safety plan, aggregate adverse event reports will be reviewed periodically to assess for potential systemic safety effects, such as cardiovascular events, neoplasms, or alteration in immune function (e.g., reports of infections to encapsulated bacteria, such as *Neisseria meningitidis*, *Streptococcus pneumoniae*, and *Haemophilus influenzae*).

The incidence and characteristics of adverse events, serious adverse events, and laboratory abnormalities will be assessed as described within this protocol. *An iDMC will monitor patient safety and study conduct on an ongoing basis (see Section 3.1.3). The iDMC shares with the Sponsor the responsibility to monitor overall patient safety in relation to the IMP, lampalizumab.*

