5.1.1 Safety Procedures

A finger-counting test will be conducted for each patient by the physician within 15 minutes following study treatment; hand-motion and light-perception tests will be performed when necessary. Following the study treatment, IOP will be measured between 30 and 50 minutes after study treatment by the site staff for the study eye only; if the IOP is increased by ≥ 10 mmHg from the pre-injection IOP value, IOP will be measured again at 60–80 minutes post-injection. If there are no safety concerns, the patient will be permitted to leave the clinic. If the IOP value is of concern to the investigator, the patient will remain in the clinic and will be managed in accordance with the investigator's clinical judgment. Both the last post-injection IOP measured prior to any intervention for increased IOP (if applicable) and the last post-intervention IOP value (if applicable) will be recorded on the appropriate eCRF. If applicable, an Adverse Event eCRF should also be completed (see Section [5.2.1](#)).

If the study eye is treated with a Lucentis injection during the same visit that study treatment is administered, the treatment with Lucentis has to be performed first. Please measure and record the post-Lucentis treatment IOP value on the eCRF, irrespective of the subsequent study treatment administration.

Detailed ocular examinations, including indirect ophthalmoscopy and slit-lamp examination, will be performed throughout the study. Blood samples will be obtained from all patients at selected timepoints in order to measure serum lampalizumab concentrations and levels of antibodies to lampalizumab and other biomarkers (see [Appendix 1](#)). The optional aqueous humor samples will be obtained from the patients who consent to this procedure and sample collection.

Patients discontinued from the study will be asked to return for early termination visit assessments after a minimum of 30 days has elapsed following the last study treatment visit (see [Appendix 1](#)). The visit will include assessment of all adverse events (serious and non-serious; ocular and non-ocular). Serious adverse events will be reported in compliance with GCP guidelines.

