6.3 SAFETY ANALYSES

The safety analyses will include patients enrolled in this study who receive at least 1 dose of study drug *in all patients and* according to treatment received in the parent study.

Verbatim descriptions of treatment-emergent adverse events will be coded, and their incidence will be summarized, as appropriate. Separate summaries will be generated for serious adverse events, deaths, adverse events leading to discontinuation of study drug, and adverse events judged to be related to lampalizumab. In addition, separate

summaries will be prepared for systemic (non-ocular) and ocular adverse events. Descriptive summaries will be generated for VA and IOP. All patients will receive lampalizumab treatment in this study; therefore, caution must be taken when interpreting safety results as there is no inactive/sham treatment group for comparison.

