Appendix 1 Schedule of Assessments (cont.)

Table 1 Study Flowchart for Q4W Arm: Day 1, Week 4 through Week 52, and Early Termination (cont.)

- ⁿ Finger-counting test followed by hand-motion and light-perception tests (when necessary) will be performed by the physician within 15 minutes after study drug treatment. At study drug treatment visits, post-treatment IOP measurement in the study eye only between 30 and 50 minutes post-treatment with study drug will be performed by the qualified site staff (except for the VA examiner). If the IOP is increased by ≥ 10 mmHg from pre-treatment, the IOP will be measured again 60–80 minutes post-treatment. If there are no safety concerns, the patient will be permitted to leave the clinic. If the IOP value is of concern to the investigator, the patient will remain in the clinic and will be managed in accordance with the investigator's clinical judgment. Both the last post-treatment IOP measured prior to any intervention for increased IOP (if applicable) and the last post-intervention IOP (if applicable) will be recorded on the Post-Treatment IOP eCRF. If the study eye is treated with a Lucentis[®] injection during the same visit as study drug treatment, the treatment with Lucentis must be performed first. Measure and record the post-Lucentis treatment IOP value on the eCRF.
- ^o Record on the *concomitant medications log* any concomitant medications (i.e., any prescription medications or over-the-counter preparations **other than** protocol-specified procedural medications, such as proparacaine) that patients *continue* taking (no stop date) *after the Week 96 visit of the parent study is completed or concomitant medications that patients started during the extension study. Record concomitant medications* through the patient's early termination visit.
- ^p Any adverse events ongoing *after the Week 96 visit* from the parent study *is complete* should be transcribed to OLE Adverse Events eCRF log. *After the Week 96 visit completion for the parent study, new adverse events will be recorded in the extension study through a minimum of 30 days after the last dose of study drug or the last study visit, whichever is later. Adverse events assessed by the investigator as related to the study drug should be followed until the event resolves or until the event is assessed as irreversible, chronic, or stable, even if patient's participation in the study has ended.*

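### When a rise in IOP triggers a repeat reading, the protocol does not require the triggering 30–50 minute value to be recorded, so rises that settle untreated may be missing from the IOP data

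*Combined protocol and SAP*

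**What the plan says.** Section 4.5.4.1 sets the first reading: "IOP will be measured between 30 and 50 minutes after study treatment by qualified site staff (except for the VA examiner) for the study eye". Section 5.1.1 gives the trigger for a second: "if the IOP is increased by ≥ 10 mmHg from the pre-injection IOP value, IOP will be measured again at 60–80 minutes post-injection".

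Two values are then named for the eCRF. The first is "the last post-injection IOP measured prior to any intervention for increased IOP (if applicable"). The second is "the last post-intervention IOP value (if applicable) will be recorded on the appropriate eCRF". Section 5.1.1 repeats the rule. So do the Appendix 1 footnotes n (Table 1), k (Table 2) and o (Table 3), which begin "Both the last post-treatment IOP measured prior to any intervention for increased IOP (if applicable") and name the Post-Treatment IOP eCRF as the form. None of these five places asks for the reading that triggered the repeat, for each reading, or for the highest one.

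An Adverse Event eCRF is also to be completed where applicable, with a pointer to Section 5.2.1.

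Section 5.1 lists "transient and/or sustained elevation of IOP" among the potential ocular safety issues. On analysis, Section 6.3 says: "Descriptive summaries will be generated for VA and IOP". It does not say whether pre- or post-injection values are meant, at which time point, or against which threshold.

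**The concern.** The rule keeps the last pre-intervention reading, and a second reading is taken only in patients whose first was raised. The time of the recorded value therefore depends on the outcome: 30–50 minutes in a patient without a rise, 60–80 minutes in a patient with a rise who is not treated before the repeat. A post-injection summary that pools the two mixes time points in an outcome-dependent way.

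The reading most exposed to loss is the one that shows a short-lived rise. Long-term safety is the primary objective and transient elevation is named as an issue of interest, yet a rise that settles on its own can leave no trace on the IOP form. If the iDMC works from the eCRF data at its roughly six-monthly reviews (Section 3.1.3), it would see the same reduced record.

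The adverse event route is an uncertain backstop. Under Section 5.2.1 a worsened clinical test counts when it has symptoms or changes treatment, and a silent rise that settles untreated does neither. The broader criterion of an unfavorable, unintended sign could cover it, but no IOP threshold for adverse event reporting is given, so capture rests on the investigator's judgment.

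**Working it through.** The documents give no rate of IOP rise, no spread and no rate of decay, so there is no stated figure to reproduce. The check applies the recording rule to cases and then expresses the loss as a formula.

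**Inputs from the protocol.** First reading at 30–50 minutes; trigger of 10 mmHg or more above pre-injection; repeat at 60–80 minutes; recorded values are the last before intervention and the last after it (Sections 4.5.4.1 and 5.1.1, Appendix 1). Up to 1800 patients (Section 3.1.2). The rule applies at each scheduled injection visit through Week 96: 1 + 96/4 = 25 per patient on Q4W, 1 + 96/6 = 17 on Q6W.

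**Step 1: the rule case by case** (hypothetical values in mmHg, pre-injection 15 throughout).

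| Case | 30–50 min | 60–80 min | Intervention | Recorded | Effect |
|---|---|---|---|---|---|
| 1 | 22 | not taken | none | 22 | nothing lost |
| 2 | 32 | 20 | none | 20 | rise of 32 − 15 = 17 appears as 20 − 15 = 5 |
| 3 | 45 | not taken before treatment | before the repeat, then 22 | 45 and 22 | triggering value kept |
| 4 | 32 | 36 | after the repeat, then 24 | 36 and 24 | highest value kept |

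Of these, only case 2 loses a rise: IOP falls by the repeat with no intervention in between.

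**Step 2: share of measured rises missed.** Let i be the share of patients with a rise of 10 mmHg or more who are treated before the repeat, and d the share of the remainder whose rise is below 10 mmHg by the repeat. A rise is invisible in the recorded pre-intervention value when both conditions hold:

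missed share = (1 − i) × d

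Both i and d are assumptions.

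| | d = 0.3 | d = 0.6 | d = 0.9 |
|---|---|---|---|
| i = 0 | 30% | 60% | 90% |
| i = 0.1 | 27% | 54% | 81% |
| i = 0.3 | 21% | 42% | 63% |

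A rise that has fallen but still stands at 10 mmHg or more is not counted as missed here, although its recorded size is reduced.

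**Step 3: illustration in counts.** Take one injection visit with 1800 patients and assume 5% have a rise of 10 mmHg or more: 1800 × 0.05 = 90 rises. The number visible in the recorded pre-intervention value is 90 × (1 − missed share). At i = 0 and d = 0.9 this is 90 × 0.10 = 9. At i = 0.3 and d = 0.3 it is 90 × 0.79 ≈ 71.

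**Step 4: with both readings recorded.** Every measured rise of 10 mmHg or more is on the form, so the missed share is 0 for any i and d.

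**The case against.** The strongest reply is that the form itself is not in the documents. The recording sentence directly follows the text on an IOP that worries the investigator and is qualified by applicability. It can be read as saying what to enter around an intervention, without excluding other readings. Post-treatment IOP is a scheduled assessment at every injection visit, and Section 7.1 leaves the eCRF specifications to the Sponsor. The actual form may already hold both readings. That possibility stands. But five places in the protocol state the rule and none requires the triggering value, so a site that follows the text need not enter it.

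It is also fair that an adverse event report remains possible, since Section 5.3.1 requires all adverse events noted by study personnel to be recorded. This route feeds the primary objective directly. It stands as a partial safeguard, subject to judgment. Sustained elevation is not affected, because pre-treatment IOP is measured at every injection visit.

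A reader might go further and infer that every patient with a rise of 10 mmHg or more loses the peak value. The documents do not support this. Treatment before the repeat preserves the first reading, a higher repeat is itself recorded, and the post-intervention value is recorded as well. Nor is the 30–50 minute reading shown to be the peak, since no earlier reading is scheduled.

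**Conclusion.** The point holds as a gap in the recording rule. Where a repeat is taken, IOP has fallen by then and no intervention came first, the protocol does not require the 30–50 minute value on the Post-Treatment IOP eCRF. Transient rises may then be absent from the IOP data, and recorded post-injection values come from times that depend on the outcome.

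A reader might infer that the IOP summary is bound to be biased downward, or that the study cannot report transient rises. That goes too far. Section 6.3 does not say which IOP values are summarized, the eCRF layout is not shown, an adverse event may be filed, and the direction is downward only where rises fall by the repeat.

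The size is unknown. The range of 21–90% rests wholly on the assumed i and d, and shows that the loss could be small or large. The case for acting does not depend on it: a reading already taken for a named safety issue should not be left unrecorded. This is an inexpensive improvement that should be made; it does not invalidate the design.

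**What to change.** In Sections 4.5.4.1 and 5.1.1 and in Appendix 1 footnotes n (Table 1), k (Table 2) and o (Table 3), require the 30–50 minute IOP and, if taken, the 60–80 minute IOP to be recorded, each with its clock time, in addition to the last pre-intervention and last post-intervention values. Bring the Post-Treatment IOP eCRF into line if it does not already hold these fields.

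In Section 6.3, specify three post-injection summaries: the change from pre-injection to 30–50 minutes, the maximum recorded pre-intervention post-injection IOP, and the share of patients with a rise of 10 mmHg or more.

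The cost is edited text in five places, up to two timed entries per injection visit, and one more table. No measurement, visit or clinical rule changes, and summaries based on the last value remain possible. The change is best made early, because values not entered would be hard to recover later across up to 300 sites.
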